8.2.3 Collection and Follow up of Adverse Events

All AEs, however minor, will be documented in the CRF whether or not the Investigator considers the event to be treatment related.

The AE reporting period will be from consent until the subject's final study visit. In addition, any untoward event that may occur subsequent to the reporting period that the Investigator assesses as possibly, probably or definitely related to the study drug medication should also be reported as an AE.

AEs may be directly observed, reported spontaneously by the subject or by questioning the subject at each study visit.

All AEs should be followed up until they are resolved or the subject's participation in the study ends (i.e. until the final CRF is completed for that subject). In addition, all serious and non-serious AEs assessed by the Investigator as possibly related to the investigational medication should continue to be followed up to last subject visit. Such events should be followed until resolution, until no further change can reasonably be expected, or until 30 days following last subject visit.

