8.2.4 Recording and Reporting of SAEs and SUSARs

Definition of an SAE can be found in section 8.1.

The SAE should be reported to the sponsor using the study specific Safety Event Reporting Form (SERF), within 24 hours of a member of the study team becoming aware of the event via e-mail to [contact] or via the fax number provided on the SERF.

All SAEs occurring from the time of written informed consent until 30 days post cessation of trial treatment must be recorded on the study specific SAE Form and sent to the sponsor within 24 hours of the research staff becoming aware of the event.

For each SAE the following information will be collected in the SERF:

- full details in medical terms and case description
- event duration (start and end dates, if applicable)
- action taken
- outcome
- seriousness criteria
- causality (i.e. relatedness to trial drug / investigation), in the opinion of the Investigator
- details of the reporter(s)

Any change of condition or other follow-up information should be sent to the sponsor in a follow up SERF as soon as it is available or at least within 24 hours of the information becoming available. Events will be followed up until the event has resolved or a final outcome has been reached.

The Sponsor representative (CI) will assess whether events suspected to be related to IMP-treatment would be considered expected or unexpected (using the formally approved and implemented version of the reference safety information (RSI) for either Syntuza® or Biktarvy®).

All SAEs assigned by the PI or delegate (or following central review) as both suspected to be related to IMP-treatment and assessed by the CI as unexpected will be classified as SUSARs. The sponsor will inform the CA, the IRB/IEC and the funder as appropriate of SUSARs within the required expedited reporting timescales. The sponsor will update the Eudravigilance database, as required.

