2. **Hepatitis B and C.** *Significant increase in ALT over baseline (flares) have been documented after beginning antiretroviral therapy/regimen with HBV co-infection as well as after interruption of antiretroviral therapy/regimen (especially in patients with HBV on a 3TC- or tenofovir-containing regimen). After immune recovery HBV "flares" may occur if HBV is not being concomitantly treated, although there are other potential reasons to consider. These include:*
 - a) spontaneous HBeAg seroconversion;
 - b) treatment induced exacerbation of the underlying disease;
 - c) hepatotoxic effects of treatment;
 - d) withdrawal of active HBV drug;
 - e) development of resistance and return of replication, and/or
 - f) superimposed and unrelated acute liver disease (e.g. hepatitis A)

Liver biopsy may be helpful in determining evidence of drug related (eosinophilic infiltrate) vs. acute viral hepatitis (hepatocyte swelling with lobular inflammation).

Biopsy may also grade and stage chronic viral hepatitis. IRIS is less well-defined in HCV co-infection, and increases in liver enzymes on antiretroviral therapy/regimen may be multifactorial as well.

3. **Herpes simplex virus (HSV).** *The development of unusual presentations of HSV following the initiation of antiretroviral therapy/regimen attributed to immune reconstitution have been rarely described.*

Localized HSV vesicles may occur within 8 weeks of initiating ART among persons with no prior history and no new source contact to attribute it to. Symptoms and signs are frequently consistent with a primary infection. Chronic erosive or ulcerative lesions of the genitals have been described in individuals who had prior histories of genital HSV. The appearance and clinical course of the lesions attributed to immune reconstitution appeared inconsistent with these patients' previous HSV presentations. Proctitis has also been reported [1,18,19]. Routine viral cultures may or may not yield HSV though histochemistry studies may show evidence of HSV antigens in the absence of a positive viral culture. Histopathology in some cases may demonstrate an inflammatory infiltrate with unusual prominence of plasma cells and eosinophils. Response to antivirals appears to be variable.

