5.2.3 Safety Population

Safety analysis set: all participants who are exposed to a study intervention. Participants will be analysed according to the planned randomised intervention.

The safety analysis set is used to analyse the endpoints and assessments related to safety.

Safety analysis set and DPS1 will be used to present safety data.

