8. SAFETY ANALYSES

Endpoints

Safety endpoints include the following endpoints:

- Cumulative incidence of any adverse events (AEs: grade \geq 2), separately grade 2, 3 and 4 AE
- Cumulative incidence grade 3 or AEs
- Cumulative incidence of drug-related AEs (all grade)
- Cumulative incidence of drug-related grade 3 and 4 AEs
- Cumulative incidence of serious adverse events (SAE)
- Cumulative incidence of AE leading to study/treatment
- Cumulative incidence of laboratory toxicities
- Death

Participants with multiple adverse events on a given day will be considered as having one adverse event on that day. Adverse events occurring before the initiation of study treatment (baseline) will not be considered in the analysis.

Descriptive statistics and graphical representation

All analyses on safety endpoints will be performed on the Safety analysis set. All observed data will be included in the analysis set.

Any AE (grade \geq 2), grade 3 or 4 AE, SAE, drug-related SAE, grade 2, 3 and 4 AEs, drug-related grade 3/4 AE, drug-related AEs (all grade), discontinuation of study/treatment due AEs, laboratory toxicities and death will be summarized with the total number of events, number and percentage of participants with at least one event and the incidence rates per 100 person-years of these events by treatment group (BIC versus DRV/c). The most frequent drug-related grade 3 or 4 AEs will be reported.

Statistical methodology

The incidence rates of each endpoint of interest will be calculated by the total number of events from baseline to week 48 visit divided by the total number of person-years. In this analysis, the entire

follow-up will be considered (i.e. follow-up will begin at baseline and continue until the week 48 visit, study discontinuation or death, loss to follow-up; whichever occurs first). The duration in years of participation for each subject will be calculated by the difference between the date of the last observation and the date of date of study treatment initiation plus one, divided by 365.25. The person-years is the total sum of the number of years that each member of a study population has been under observation.

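### The SAP's safety analysis stops at the week-48 visit or study exit, so adverse events, SAEs and deaths that the protocol collects after that point enter no planned table

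*Combined protocol and SAP*

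**What the plan says.** SAP section 8 defines the safety rates as "calculated by the total number of events from baseline to week 48 visit divided by the total number of person-years". The same paragraph spells out the window: "follow-up will begin at baseline and continue until the week 48 visit, study discontinuation or death, loss to follow-up; whichever occurs first". Each participant's person-time is the "difference between the date of the last observation and the date of date of study treatment initiation plus one, divided by 365.25".

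Two other SAP statements bear on this. The descriptive paragraph of section 8 says "All observed data will be included in the analysis set", and section 5.2.3 says "Safety analysis set and DPS1 will be used to present safety data". Under section 5.2.1, DPS1 keeps observations made after study drug is stopped or rescue therapy is started.

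The week-48 limit also stands in the endpoint lists: SAP 2.2.2 for graded adverse events and death, and protocol v5.0 section 2.4.2 for graded signs, symptoms and laboratory toxicities. Table 7, the only safety table, shows events, participants and rates by arm, with SAE and death rows. It has no column for the period after week 48 or after treatment.

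On collection, protocol v5.0 section 8.2.3 says "The AE reporting period will be from consent until the subject's final study visit". Section 8.2.4 requires SAEs from consent "until 30 days post cessation of trial treatment must be recorded". Section 3 places the last visit 30 days after week 48. The flowchart in Appendix 1 allows 7 days either side and marks adverse event assessment, haematology and clinical chemistry at that visit; SAP 3.3 repeats this schedule.

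**The concern.** The data collection and the analysis end on different dates. The protocol asks sites to record safety events for about a month beyond the point at which the SAP stops counting, and no part of the SAP picks those records up.

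At stake is a complete between-arm account of serious harm. The clearest case is a participant who leaves the study on stopping treatment and dies shortly afterwards, before week 48 would have been reached. The protocol collects that death and the SAP endpoint covers it in time, but section 8 closes that participant's follow-up at study exit, so the death row of Table 7 would miss it.

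**Working it through.** The documents state no figure on this point, so there is none to reproduce. The check compares the two windows and then sizes the difference.

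**1. Which events fall between the windows**

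| Event | Collected by the protocol | Counted under SAP 8 |
|---|---|---|
| Before week 48, on study drug | Yes | Yes |
| Before week 48, drug stopped, still in the study | Yes (section 6.5 asks for visits to week 48) | Yes, through DPS1 |
| SAE or death before week 48, after study exit, within 30 days of treatment stopping | Yes (8.2.4) | No: follow-up ended at study discontinuation |
| AE, SAE or death after the week-48 visit, up to the follow-up visit | Yes (8.2.3, Appendix 1) | No: follow-up ended at week 48 |

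The gap is the last two rows. The third applies only to participants who leave the study within 30 days of stopping drug; for those who leave later, that month has already been counted. Protocol section 8.4 takes unrelated deaths more than 30 days after the final dose out of SAE reporting, so only some later deaths will be known.

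**2. Whether another SAP section covers the gap**

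SAP 5.3 uses the follow-up visit to fill missing week-48 values of continuous endpoints and to decide censoring. SAP 10.2.3 uses it to describe viral load from week 48 to week 52. Neither covers adverse events, SAEs or deaths.

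**3. Whether the all-observed-data wording extends the window**

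DPS1 concerns data after study drug stops. It says nothing about time after week 48 or after study exit, whereas the follow-up sentence in section 8 names the end dates explicitly. The specific sentence governs.

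**4. Size of the post-week-48 part**

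Inputs: 48 weeks = 336 days; follow-up visit at 30 days, range 23 to 37 (Appendix 1); 440 enrolled and 404 evaluable (SAP section 4).

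- Share of a completer's time: 30 / (336 + 30) = 30/366 = 8.2%.
- Visit window: 23/359 = 6.4%; 37/373 = 9.9%.
- Person-years if all 440 complete: 440 × 30 / 365.25 = 36.1, on top of 440 × 337 / 365.25 = 406.0 to week 48.
- With 404 completing: 404 × 30 / 365.25 = 33.2.

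The post-exit part cannot be sized. The planned drop-off of about 7.5% a year would be 440 × 0.075 = 33 participants, but it is not broken down by reason, and those lost to follow-up may never have their 30 days observed.

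**5. Matching of events and person-time**

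Person-time runs to the date of last observation. If that were taken as the follow-up visit while events stop at week 48, each completer's rate would be multiplied by 336/366 = 0.918 (336/359 = 0.936 to 336/373 = 0.901). With similar attendance in both arms the rate ratio would hardly move, but the reported rates would be too low.

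**The case against.** The strongest reply is that the SAP does what the protocol asks. The safety endpoint runs through week 48 in both documents, and neither promises a comparison to 30 days after the last dose. Collecting SAEs beyond that date serves pharmacovigilance, and those SAEs still reach the sponsor, the annual safety report (protocol 8.8) and the unblinded DSMB review (8.3.4 and 12). This stands as a defence of week 48 as the main window. It does not explain the loss of a death after study exit but before week 48, and safety reports to oversight bodies are not the SAP's comparison by arm.

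A second reply is that the explicit limit sits in the rate methodology, while the count and percentage columns of Table 7 carry no stated cut-off and section 8 speaks of all observed data. This stands in part: the wording needs clarifying. Given the endpoint list, week 48 remains the likelier reading for the counts too.

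A third reply is that completers move to local treatment at week 48 (protocol 7.10), so later events arise on unrandomised regimens and are hard to attribute to an arm. This stands, and is why the added summary should be separate and labelled.

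A reader might also infer from the hepatitis text in Appendix 6 that ALT flares on withdrawal are being missed in completers. That text concerns interruption of antiretroviral therapy, and the plan does not stop antiretroviral therapy at week 48.

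**Conclusion.** The point holds as a gap in safety reporting. Adverse events, SAEs and deaths collected after week 48, and SAEs and deaths collected after study exit, enter no SAP table. The part that conflicts with the SAP's own endpoint is deaths after study exit but before week 48.

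The post-week-48 window is 8.2% of a completer's time (6.4% to 9.9%) and at most about 36 person-years, assuming all 440 complete and attend at 30 days.

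Three stronger readings are tempting and not supported:

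- A reader might infer that the whole 30-day post-treatment period goes unreported. It does not: participants who stop drug and remain in the study are counted to week 48, although their off-drug events are not shown separately.
- A reader might want to put a number on the missing SAEs or deaths. The documents give no event rate for this period, and Appendix 6 places much IRIS in the first months of therapy, so carrying an average rate forward would be guesswork.
- A reader might infer that the arms are understated by different amounts. Nothing in the documents shows this, and a toxicity that led to stopping drug already has its own row in Table 7.

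The primary analysis, sample size and power do not depend on any of this.

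**What to change.** Amend SAP section 8 before sign-off, which section 5.1 allows:

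1. Keep the week-48 table as the main safety analysis.
2. Count every known death up to week 48 in its death row, including deaths after study exit. If a death rate is also shown, run everyone's person-time to the last date on which vital status is known, up to week 48.
3. Add one supplementary table or column, by arm, of grade 3/4 adverse events, SAEs and deaths from week 48 or study exit to the later of the follow-up visit and 30 days after the last dose. Label it post-treatment, because participants may by then be on local treatment.
4. State that person-time ends on the same date as event counting, and that DPS1 and the all-observed-data wording do not move that date.

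A breakdown by HBV status is optional; the documents do not give the size of that subset.

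The cost is one extra table and a few sentences, using data the protocol already collects. The drawback is that events on unrandomised local treatment could be over-read, which the separate label is meant to prevent.

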3. STUDY METHODS

3.1 GENERAL STUDY DESIGN AND PLAN

LAPTOP study is an international, open-label, randomised, two arm, multicentre trial over 48 weeks to compare two strategies for HIV-1 infected patients with advanced disease.

Eligible patients will be randomised to receive either an integrated inhibitor containing regimen (B (50mg)/F (200mg)/TAF (25mg) [1 pill administered orally once daily for 48 weeks]) or a boosted PI regimen (D (800mg)/C (150mg)/F(200mg)/TAF (10mg) [1 pill administered orally once daily for 48 weeks]). Randomisation is stratified by country and baseline CD4 cell count (<50 cells/ μ L, 50-199 cells/ μ L, or \geq 200 cells/ μ L).

[figure not shown]

Figure 1: Study design

Study participants will be ART-naïve, HIV-1-infected individuals aged 18 or older who have at entry HIV viral load > 1000 copies/ml and at least one of the following: i) have AIDS with any CD4 cell count; ii) have severe bacterial infection (BI) and must have a CD4 cell count < 200/µl within 30 days prior to study entry; iii) are asymptomatic with CD4 cell count < 100/µL within 30 days prior to study entry; iv) are currently receiving treatment for OI. Women who were pregnant or breastfeeding or who declined a contraceptive method at screening were not eligible.

After the screening visit, participants will be seen at baseline, when they initiated c-ART and weeks 4, 8, 12, 24, 36 and 48, as well as a follow-up visit 30 days following the week 48 visit.

At each visit, participants will have routine safety monitoring as well as measurement of plasma HIV-1 RNA viral load, CD4, CD8 cells counts and a deep sequence resistance test. In the event of virological failure, local resistance tests should be performed on the first sample, and participants should discontinue study treatment and receive rescue therapy at the investigators' discretion.

Quality of life (QoL) questionnaire (EuroQoL EQ-5D-3L) and HIV Symptom Index (HIV-SI/SDM) questionnaire will be administrated at each visit from baseline.

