The follow-up will begin at baseline and continue until the week 48 visit, study discontinuation, loss to follow-up, or onset of the composite primary endpoint events; whichever occurs first. Participants lost to follow-up or who have discontinued the study when they are endpoint free at time of leaving the study will be censored at the date of last observation.

The effect of study treatment will be assessed using Cox regression model with treatment group and adjustments for stratification factor (country/group of neighbouring countries and baseline CD4 cell

counts ($<50/\mu\text{L}$ or $\geq50/\mu\text{L}$), as the sample size would not allow use of the stratification factors of randomisation (country and baseline CD4 in three categories (<50 ; $50-199$; $\geq200/\mu\text{L}$)). An adjusted hazard ratio (HR) and the associated 95% Confidence Interval (CI) will be calculated. Separate analyses for each component of the primary endpoint will be done. All P-values will be two-tailed with a significant level at 5%.

A sensitive analysis will be performed with the per-protocol population and DPS2.

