7.2.7 Incidence of IRIS

Endpoints

The endpoint is the first occurrence of IRIS over the 48-week visit. IRIS diagnosed at baseline will not be considered in the analysis.

Descriptive statistics and graphical representation

The analyses will be performed with the mITT population and DPS1. Data will be summarized with the number and percentage of participants with an IRIS. Kaplan-Meier curves will also be plotted.

Statistical methodology

The incidence of IRIS will be estimated with the Kaplan-Meier method. The follow-up will begin at baseline (date of study treatment initiation) and continue until the week 48 visit, study discontinuation or death, loss to follow-up, or onset of IRIS; whichever occurs first.

The effect of study treatment will be assessed using Cox regression model with treatment group and adjustments for stratification factor (country/group of neighbouring countries and baseline CD4 cell counts (<50 or $\geq 50/\mu\text{L}$)). An adjusted hazard ratio (HR) and the associated 95% Confidence Interval (CI) will be calculated.

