The incidence rates of each endpoint will be compared between the treatment groups (BIC versus DRV/c) with a Poisson regression model adjusted for stratification factor (country/group of neighbouring countries and baseline CD4 cell counts (<50 or \geq 50/ μ L)). The incidence rates ratio and the associated 95% confidence interval will be calculated. All P-values will be two-tailed with a significant level at 5%.

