10. OTHER ANALYSES

10.1 OTHER SECONDARY ENDPOINTS

10.1.1 ART and/or opportunistic infection/bacterial infection treatment changes and/or dose modifications due to toxicities and/or DDI with ART, and/or IRIS through week 48

Endpoint

The endpoint is the proportion of patients with ART treatment changes and/or dose modifications due to toxicities and/or DDI with ART, and/or IRIS through week 48.

Descriptive statistics and graphical representation

The analyses will be performed with the mITT population and DPS1. Data will be summarised with the number and percentage of participants with ART or OI/BI treatment changes or dose modifications due to toxicities and DDI and IRIS through week 48. The list of patients with the event of interest will be reported in a table, including the previous and the current treatment, start date, end date and the reason for change.

Statistical methodology

The percentage of patients with ART n treatment changes due to toxicities and/or DDI with ART, and/or IRIS will be estimated by the number of patients with the event of interest divided by the total number patients in ITT population. The effect of study treatment on the proportion of patients with ART treatment changes due to toxicities and/or DDI with ART, and/or IRIS at week 48 will be assessed using a logistic regression model with treatment group and adjustments for stratification factor (country/group of neighbouring countries and baseline CD4 cell counts (<50 or \geq 50/ μ L)). An adjusted odds ratio (OR) and the associated 95% Confidence Interval (CI) will be calculated. Similar analyses will also be performed separately for each component (toxicities, DDI, and IRIS). If no events were observed in a group, the comparison will be made using Fisher's exact test.

10.1.2 Health care resource use, through week 48

Endpoint

The endpoint is the proportion of patients with health care resource use, through week 48.

Descriptive statistics and graphical representation

The analyses will be performed with the mITT population and DPS1. Data will be summarised with the number and percentage of participants with health care resource use, including total inpatient days and emergency room visits through week 48.

Statistical methodology

The percentage of patients with health care resource use, including total inpatient days and emergency room visits will be estimated by the number of patients with the event of interest divided by the total number patients in ITT population.

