10.1.6 Change from baseline in plasma and urine laboratory parameters

Endpoints

The endpoints are the change from baseline plasma and urine laboratory parameters

Descriptive statistics and graphical representation

The analyses will be performed with the mITT population and DSP1.

Data will be summarised by mean and standard error. The evolution will be described by boxplots for each treatment group at each time point.

Statistical methodology

The changes from baseline in haematology, chemistry, lipid and glycaemia will be compared between the two treatment groups using mixed models for repeated measures with random intercept and slope and spatial power covariance structure due to unequal time intervals between visits, adjusted for country/group of neighbouring countries and baseline CD4 cell counts (<50 or $\geq 50/\mu\text{L}$). The model will include treatment group, time, interaction between treatment group and time, country/group of neighbouring countries and baseline CD4 cell counts (<50 or $\geq 50/\mu\text{L}$). Time will be modelled as categorical variables.

All p-values will be two-tailed, with a significant level of 0.05.

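### SAP 8 tests total adverse-event counts with a plain Poisson model; if patients differ in event-proneness, confidence intervals for frequent recurrent AEs are too narrow

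*Combined protocol and SAP*

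**What the plan says.** SAP 8 defines the safety rates as event rates: "The incidence rates of each endpoint of interest will be calculated by the total number of events from baseline to week 48 visit", divided by total person-years. The whole follow-up counts, not only the time to a first event. The one rule on repeats within a patient is "Participants with multiple adverse events on a given day will be considered as having one adverse event on that day", so events on different days all enter the numerator.

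The comparison is then: "The incidence rates of each endpoint will be compared between the treatment groups (BIC versus DRV/c) with a Poisson regression model". It is adjusted for country or country group and for CD4 (below 50, or 50 and above), and gives a rate ratio, a 95% CI and two-sided 5% p-values. The endpoints include any grade 2 or higher AE, drug-related AEs, SAEs, laboratory toxicities and death.

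Neither SAP 8 nor the general and software sections mention a dispersion check, scale parameter, sandwich variance, negative binomial model or patient random effect for these counts. Elsewhere the SAP does allow for repeated observations within a patient: GEE for the CD4 proportions (7.2.5), and mixed models for CD4/CD8 ratio, quality of life and laboratory values (7.2.6, 10.1.3, 10.1.6).

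**The concern.** A Poisson model with those covariates treats all patients in the same arm and stratum as having one common event rate. Eligibility mixes AIDS at any CD4 count, severe bacterial infection, very low CD4 with or without symptoms, and current treatment for an opportunistic infection. Entry group is tabulated at baseline but is not in the model. Some patients are likely to have many more events than others in their stratum, although the documents do not quantify this.

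If so, the variance of the counts exceeds the Poisson variance. The rate ratio is still estimated without bias from this source, but its standard error is too small. A few event-prone patients falling by chance in one arm could then produce an apparently significant difference in AE rate. Tolerability is a stated secondary objective and the trial is open-label, so such a result would be read as a finding about the regimens.

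**Working it through.** **No stated figure to reproduce.** The plan gives no expected AE rate, dispersion or safety precision. As a check on the numbers of patients used, the trial's own size was re-derived:

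- Events: 4(1.96 + 0.8416)² / [ln 1.606 − ln 0.909]² = 96.9 (stated 97).
- Evaluable patients: 97/0.24 = 404 (stated 404).
- Enrolled: 404/0.925 = 437 (stated 440).

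**Inputs from the documents.** 220 per arm and 7.5% per year drop-out (SAP 4), 48 weeks of follow-up (SAP 3.1), two-sided 5% and the covariates above (SAP 8). Forty-eight weeks is 336/365.25 = 0.920 year. With drop-out hazard −ln(0.925) = 0.0780 per year, mean follow-up is (1 − e^(−0.0780×0.920))/0.0780 = 0.888 year.

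**Assumptions.** Event rates of 0.1 to 3 per person-year; patient rates varying by a gamma multiplier with mean 1 and variance φ of 0, 0.5 or 1; four country groups.

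**Formula.** With mean count μ = rate × 0.888, the count variance is μ + φμ² = μ(1 + φμ). The correct standard error of the log rate ratio is the Poisson one times √(1 + φμ). A nominal 5% test then rejects with probability 2[1 − Φ(1.96/√(1 + φμ))].

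**Clinical AE counts, no true difference.** Simulation: 6000 trials per setting, adjusted Poisson model with log person-years offset.

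| Rate per person-year | μ | √(1+φμ), φ=0.5 / 1 | Formula % rejected, φ=0.5 / 1 | Simulated Poisson %, φ=0 / 0.5 / 1 | Simulated robust %, φ=0 / 0.5 / 1 |
|---|---|---|---|---|---|
| 0.1 | 0.09 | 1.02 / 1.04 | 5.5 / 6.0 | 4.6 / 5.0 / 5.5 | 4.9 / 4.7 / 4.9 |
| 0.3 | 0.27 | 1.06 / 1.13 | 6.6 / 8.2 | 5.4 / 6.5 / 7.9 | 5.6 / 5.4 / 5.2 |
| 1 | 0.89 | 1.20 / 1.37 | 10.3 / 15.4 | 5.0 / 10.0 / 15.7 | 5.4 / 5.4 / 5.2 |
| 2 | 1.78 | 1.37 / 1.67 | 15.4 / 23.9 | 4.8 / 14.9 / 23.9 | 4.9 / 5.3 / 5.6 |
| 3 | 2.66 | 1.53 / 1.91 | 19.9 / 30.6 | 5.0 / 20.1 / 31.1 | 5.3 / 5.4 / 6.1 |

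The simulated ratio of robust to Poisson standard error agrees with the third column: 1.06 and 1.12 at 0.3, 1.19 and 1.37 at 1, and 1.52 and 1.90 at 3.

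A separate simulation (2000 trials per setting, five country levels) gave 10.1% and 16.2% at μ = 1, and 16.1% and 25.2% at μ = 2, for φ = 0.5 and 1. Robust or Pearson-scaled variance gave 4.4–5.6%.

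**One interval written out.** With μ = 2, φ = 0.5 and a true ratio of 1, the Poisson standard error is √(2/(220×2)) = 0.067, giving a 95% CI of 0.88–1.14. Multiplying by √2 gives 0.83–1.21.

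**Endpoints less affected.**

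- Laboratory toxicities: the visit schedule, "After the screening visit, participants will be seen at baseline, when they initiated c-ART and weeks 4, 8, 12, 24, 36 and 48", leaves six post-baseline visits. Allowing at most one event per visit and few unscheduled tests, rejection is 5.4–9.6% at underlying rates of 1 to 3 per person-year with φ = 0.5 or 1, and 1.1–2.8% (conservative) with φ = 0.
- Once-only events at assumed risks of 3% and 10%: 2.6% and 3.5%, slightly conservative.
- The recurrent-event analysis in SAP 7.2.1 uses the same model. With 202 per arm and first-event probability 97/404, rejection is 4.2% with 10 extra episodes, 5.9% with 20 and 10.1% with 40. It is 13.2% if 20 extra episodes fall in 5 patients; robust variance then gives 6.5%.

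**The case against.** **The size is assumed.** Neither the rates nor φ comes from the documents. With φ = 0 there is no problem, at 0.3 per person-year or below it is small, and the largest figures need about 3 events per person-year. This stands, which is why the conclusion is conditional.

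**Drug-related AEs may not be frequent.** Protocol 1.2.1 gives frequency bands for the bictegravir regimen in treatment-naive patients: two terms at 10% or more, seven at 1% to below 10%, and one below 1%. That population was less advanced, so the bands set no upper limit here. Still, the case is strongest for any grade 2 or higher AE; for drug-related AEs it depends on how often they recur.

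**Patient-level comparisons exist.** Protocol 9.3.3 plans Fisher's exact test for the frequency of grade 2, 3 or 4 AEs and laboratory toxicities, and protocol v5.0 post-dates SAP v0.3. At patient level, that test is immune to clustering of events. But SAP 8 does not carry it over, states no between-group test on patients with at least one AE, and would report the rate-ratio interval whether or not the test is run.

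The SAP also keeps first-event and patient-level analyses: "Separate analyses for each component of the primary endpoint will be done"; "The endpoint is the first occurrence of IRIS over the 48-week visit"; and "The effect of study treatment on the proportion of patients with ART treatment changes due to toxicities and/or DDI with ART". For laboratory values, "The changes from baseline in haematology, chemistry, lipid and glycaemia will be compared between the two treatment groups using mixed models for repeated measures". These limit reliance on the count model but do not correct it. Table 7 sets numbers of events beside numbers of patients, which would reveal concentration without changing the CI or p-value.

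**Counting rules trim repeats.** SAP 5.3 recodes partial dates to fixed days, so several partly dated AEs in one patient could merge under the same-day rule. This would tend to reduce overdispersion by an unknown amount.

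**Diffuse variation is not a few event-prone patients.** A further simulation with events concentrated in 10% of patients gave 12.6% and 26.2% in the two settings run, with robust variance at 5.0% and 6.0%. The mechanism does not depend on the gamma form.

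**Conclusion.** The concern holds, conditionally. SAP 8 counts recurrent events and tests them with a model that has no room for between-patient variation beyond country group and binary CD4. If such variation exists, intervals for frequent recurrent clinical AE counts are too narrow: the correct interval on the log scale is about 1.2 to 1.4 times as wide at 1 event per person-year and 1.5 to 1.9 times at 3, for rate variances of 0.5 to 1.

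SAE and grade 3–4 counts, if infrequent, are affected only modestly. The effect on 7.2.1 is negligible unless repeats are numerous or concentrated. Death and other once-only events need no correction. The primary analysis and sample size are untouched. This should be put right before sign-off, but it does not threaten the trial's main conclusion.

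**What to change.** In SAP 8, for endpoints that can recur, specify Poisson regression with patient-level robust (sandwich) variance, a log person-years offset and the same covariates (country group and CD4 below 50, or 50 and above). Add a cross-reference so that 7.2.1 uses the same variance if that analysis is triggered. Keep the same-day counting rule, and leave death and other once-only endpoints as they are.

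A scale parameter or negative binomial model would also address overdispersion. The sandwich variance has the advantage of leaving the endpoint and the rate-ratio estimate unchanged. What matters is that the choice is fixed before results are seen; SAP 5.1 allows updates before the final version is signed.

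The cost is one sentence, one cross-reference and one option in the code. The intervals will be wider and power lower for recurrent safety counts where overdispersion is present; where it is absent, the simulations show essentially no penalty (robust rejection 4.9–5.6% for clinical AE counts with φ = 0).
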